12.6 Appendix 6. Sample Storage and Destruction

Any blood, pharmacokinetics (PK), or pharmacodynamic (PDn) sample collected according to the Schedule of Activities ([Table 2-1](#)) can be analyzed for any of the tests outlined in the protocol and for any tests necessary to minimize risks to study subjects. This includes testing to ensure analytical methods produce reliable and valid data throughout the course of the study. This can also include, but is not limited to, investigation of unexpected results, incurred sample reanalysis, and analyses for method transfer and comparability.

All samples and associated results will be coded prior to being shipped from the site for analysis or storage. Samples will be tracked using a unique identifier that is assigned to the samples for the study. Results are stored in a secure database to ensure confidentiality.

If informed consent is provided by the subject, Amgen can do additional testing on remaining samples (ie, residual and back-up) to investigate and better understand multiple myeloma, the dose response and/or prediction of response to carfilzomib, and characterize aspects of the molecule (eg, mechanism of action/target, metabolites). Results from this analysis are to be documented and maintained, but are not necessarily reported as part of this study. Samples can be retained for up to 20 years.

Since the evaluations are not expected to benefit the subject directly or to alter the treatment course, the results of pharmacogenetic, [biomarker development,] or other exploratory studies are not placed in the subject's medical record and are not to be made available to the subject, members of the family, the personal physician, or other third parties, except as specified in the informed consent.

The subject retains the right to request that the sample material be destroyed by contacting the investigator. Following the request from the subject, the investigator is to provide the sponsor with the required study and subject number so that any remaining sample types (eg, blood) samples and any other components from the cells can be located and destroyed. Samples will be destroyed once all protocol-defined procedures are completed. However, information collected from samples prior to the request for destruction, will be retained by Amgen.

The sponsor is the exclusive owner of any data, discoveries, or derivative materials from the sample materials and is responsible for the destruction of the sample(s) at the request of the subject through the investigator, at the end of the storage period, or as

appropriate (eg, the scientific rationale for experimentation with a certain sample type no longer justifies keeping the sample). If a commercial product is developed from this research project, the sponsor owns the commercial product. The subject has no commercial rights to such product and has no commercial rights to the data, information, discoveries, or derivative materials gained or produced from the sample. See Section [12.3](#) for subject confidentiality.

12.7 Appendix 7. Hepatotoxicity Stopping Rules: Suggested Actions and Follow-up Assessments and Study Treatment Rechallenge Guidelines

Hepatotoxicity stopping rules are described in Section [7.4.1](#).

12.8 Appendix 8. Guidelines for Documenting Prior Treatment

Patients must have documented relapse after at least 1, but no more than 2 prior treatment regimens or lines of therapy for multiple myeloma. When documenting prior treatments for multiple myeloma, the following guidelines should be used:

- A new line of therapy is considered to start when a planned course of therapy is modified to include other treatment agents (alone or in combination) as a result of lack of adequate response, progressive disease (PD) (even if the level of progression has not yet met International Myeloma Working Group-Uniform Response Criteria [IMWG-URC] for PD), relapse, or toxicity.
- An increase in dose of therapy, with the intention of recapturing response in a subject who has evidence of progression on that therapy, is considered a new therapy.
- A new line of therapy is also considered to start when a planned period of observation of therapy is interrupted by a need for additional treatment for the disease.
- Examples of 1 line of therapy include:
 - Induction therapy and stem cell transplant followed by planned maintenance therapy (provided there is no intervening PD)
 - Induction therapy followed by maintenance therapy (provided there is no intervening PD)
- Documentation of at least partial response (PR) to at least 1 prior therapy

For patients with prior carfilzomib therapy, documentation of response (\geq PR) must be available for the most recent previous carfilzomib therapy as well as stop date.

Documentation that the subject was not removed from carfilzomib therapy due to toxicity must also be available. For patients with prior therapy with either carfilzomib, the start of the 6-month treatment-free interval is when either carfilzomib is discontinued even if other portions of the regimen are continued.

12.9 Appendix 9. ECOG Performance Status

Grade	Description
0	Normal activity, fully active, able to carry on all predisease performance without restriction.
1	Symptoms, but fully ambulatory, restricted in physically strenuous but ambulatory and able to carry out work of a light or sedentary nature (eg, light housework, office work).
2	Ambulatory and capable of all self-care but unable to carry out any work activities. Up and about more than 50% of waking hours.
3	Capable of only limited self-care, confined to bed or chair more than 50% of waking hours.
4	Completely disabled. Cannot carry on any self-care. Totally confined to bed or chair.
5	Dead

ECOG = Eastern Cooperative Oncology Group.

Source: Oken et al, 1982.

12.10 Appendix 10. 2018 ESH/ESC Office Blood Pressure Measurement

Patients should be seated comfortably in a quiet environment for 5 min before beginning BP measurements.
Three BP measurements should be recorded, 1–2 min apart, and additional measurements only if the first two readings differ by > 10 mmHg. BP is recorded as the average of the last two BP readings.
Additional measurements may have to be performed in patients with unstable BP values due to arrhythmias, such as in patients with AF, in whom manual auscultatory methods should be used as most automated devices have not been validated for BP measurement in patients with AF.
Use a standard bladder cuff (12–13 cm wide and 35 cm long) for most patients, but have larger and smaller cuffs available for larger (arm circumference > 32 cm) and thinner arms, respectively.
The cuff should be positioned at the level of the heart with the back and arm supported, to avoid muscle contraction and isometric-exercise dependent increases in BP.
When using auscultatory methods, use phase I and V (sudden reduction/disappearance) Korotkoff sounds to identify SBP and DBP, respectively.
Measure BP in both arms at the first visit to detect possible between-arm differences. Use the arm with the higher value as the reference.
Measure BP 1 min and 3 min after standing from seated position in all patients at the first measurement to exclude orthostatic hypotension. Lying and standing BP measurements should also be considered in subsequent visits in older people, in people with diabetes, and in other conditions in which orthostatic hypotension may frequently occur.
Record heart rate and use pulse palpation to exclude arrhythmia.

ESC = European Society of Cardiology; ESH = European Society for Hypertension

For additional antihypertensive guidance and recommendations for blood pressure goals, please refer to the 2018 Practice Guidelines for the management of arterial hypertension of the European Society of Hypertension and the European Society of Cardiology.

https://journals.lww.com/jhypertension/Fulltext/2019/02000/2018_Practice_Guidelines_for_the_management_of.37.aspx

12.11 **Appendix 11. Summary of International Myeloma Working Group - Uniform Response Criteria**

Response Subcategory	Multiple Myeloma Response Criteria
sCR	
 • Negative immunofixation on the serum and urine and • Disappearance of any soft tissue plasmacytomas and • < 5% plasma cells in bone marrow aspirate and • Normal SFLC ratio and • Absence of clonal cells in bone marrow biopsy by immunohistochemistry (kappa/lambda ratio \leq 4:1 or \geq 2:1 for kappa and lambda subjects respectively, after counting \geq 100 plasma cells)
CR	
 • Negative immunofixation on the serum and urine and • Disappearance of any soft tissue plasmacytomas and • < 5% plasma cells in bone marrow • In subjects with baseline measurable disease only by SFLC, normal SFLC ratio
VGPR	
 • Serum and urine M-protein detectable by immunofixation but not on electrophoresis or • \geq 90% reduction in serum M-protein with urine M-protein < 100 mg per 24 hours • In subjects with baseline measurable disease only by SFLC, a decrease \geq 90% in the difference between involved and uninvolved FLC levels • In subjects achieving a VGPR by other criteria, a soft tissue plasmacytoma must decrease by more than 90% in the SPD compared with baseline
PR	
 • \geq 50% reduction of serum M-protein and reduction in 24-hour urinary M-protein by \geq 90% or to < 200 mg per 24 hours • In subjects with measurable disease only by SFLC, a decrease \geq 50% in the difference between involved and uninvolved FLC levels is required in place of the M-protein criteria. • In addition to these criteria, if present at baseline, a \geq 50% reduction in the size (SPD) of soft tissue plasmacytomas is also required

Footnotes defined on the next page

Response Subcategory	Multiple Myeloma Response Criteria
SD	
 Not meeting criteria for CR, VGPR, PR, or PD
PD	
 Increase of 25% from lowest confirmed response value in 1 or more of the following: 
 Serum M-component (absolute increase must be ≥ 0.5 g/dL if the lowest M-component was < 5 g/dL) Urine M-component (absolute increase must be ≥ 200 mg per 24 hours) Only in subjects without measurable serum and urine M protein levels: the difference between involved and uninvolved FLC levels (absolute increase must be > 10 mg/dL) Increase of serum M-component of ≥ 1 g/dL if the lowest M-component was ≥ 5 g/dL Appearance of new lesion(s), $\geq 50\%$ increase from nadir in SPD of > 1 lesion, or $\geq 50\%$ increase in longest diameter of a previous lesion > 1 cm in short axis $\geq 50\%$ increase in circulating plasma cells (minimum of 200 cells per μL) if this is the only measure of disease

Page 2 of 2

CR = complete response; FC = flow cytometry; FLC = free light chain; PD = progressive disease; PR = partial response; sCR = stringent complete response; SFLC = serum-free light chain; SPD = maximal perpendicular diameter; VGPR = very good partial response

All response categories (complete response [CR], stringent complete response [sCR], very good partial response [VGPR], PR) require 2 consecutive assessments made at any time before the initiation of any new therapy, as well as no known evidence of progressive or new bone lesions if radiographic studies were performed. Radiographic studies are not required to satisfy these response requirements. Bone marrow, plasmacytoma, and skeletal survey assessments are not required to be confirmed by repeat testing.

For sCR: presence/absence of clonal cells is based upon the kappa/lambda (κ/λ) ratio in aspirate. "Measurable" disease is defined by at least 1 of serum protein electrophoresis (SPEP) ≥ 0.5 g/dL, urine protein electrophoresis (UPEP) ≥ 200 mg per 24 hours, or in subjects without measurable serum or urine M-protein, serum free light chains (SFLC) > 100 mg/L (involved light chain) and an abnormal SFLC κ/λ ratio.

Determination of PD while on study requires 2 consecutive assessments made at any time before classification of PD and/or the institution of new therapy*. Serum M-component increases of ≥ 1 g/dL from nadir are sufficient to define progression if nadir M-component is ≥ 5 g/dL.

* Every effort should be made to obtain 2 consecutive samples at any time prior to initiation of any new therapy. If not possible to obtain the second consecutive assessment to confirm disease progression before initiation of any new therapy, this confirmatory sample for disease progression may be obtained after the new therapy is initiated.

Plasmacytomas: A plasmacytoma is considered measurable if the longest diameter is at least 1 cm and the product of the cross diameters is at least 1 cm². Progression is defined as appearance of a new lesion(s), $\geq 50\%$ increase from nadir of the sum of the products of the maximal perpendicular diameter (SPD) of the measurable lesion as measured serially, or a $\geq 50\%$ increase in the longest diameter of a previous lesion > 1 cm short axis; $\geq 50\%$ increase in plasma cells if this is the only measure of disease.

For defining nadir, in the case where a value is felt to be a spurious result per physician/Independent Review Committee (IRC) discretion (eg, a possible laboratory error), that value will not be considered when determining the lowest value.

Sources: Kumar et al, 2016; Rajkumar et al, 2011; Durie et al, 2006.

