SPEP/UPEP/SFLC/SIFE/UIFE		X	X			Screening disease-specific assessments must be done within 28 days prior to enrollment and repeated if not performed within 14 days of C1D1.
Quantitative immunoglobulins		X	(X)			(X): After screening, quantitative IgA, IgD or IgE at every disease assessment in subjects with IgA, IgD or IgE myeloma, respectively. For all subjects, quantitative immunoglobulins (IgG, IgM, IgA) will be repeated every 12 months ± 2 weeks from C1D1 in subjects with PR or better, or if applicable, may be done at time of MRD assessment. May be obtained more frequently as clinically indicated
Bone lesion assessment		X	(X)			Screening evaluation may be done within 28 days prior to enrollment, if performed as a part of standard of care. (X): Repeat if worsening clinical symptoms suggest PD or as clinically indicated.
Extramedullary Plasmacytoma evaluation		(X)	(X)			(X): Will be done at screening only if clinically suspected. Screening evaluation may be done within 28 days prior to enrollment, if performed as a part of standard of care. For subjects with a history of plasmacytoma, clinical assessment will be performed locally every 28 (± 7) days from C1D1. Radiological exam will be performed only to confirm a response of PR or better, or to confirm PD, or as clinically indicated (see Section 9.2.2.5 for more details).
Bone marrow aspirate	FISH analysis for cytogenic risk	X				To be collected no later than C1D1 predose (ie, screening). An informative result that was obtained as part of SOC within 45 days prior to enrollment may be used.
	To confirm CR or sCR		(X)			(X): As clinically indicated. Bone marrow biopsy is required to confirm sCR.
	For MRD[-]CR assessment	X	(X)			At screening AND (X): at suspected CR or better (12 months ± 4 weeks from start of treatment, unless performed within 4 months prior to scheduled landmark assessment) AND (X) Subjects with a MRD[-]CR response at the first time point should have the subsequent MRD assessment 12 months ± 4 weeks after the earlier assessment, if subjects have not relapsed nor started new antimyeloma therapy prior to this subsequent MRD assessment.

Footnotes defined on last page of the table

Table 2-1. Schedule of Activities

Assessment	SCR ^a	Treatment Cycle Days				SFU ^b	LTFU	Notes
		1	8	15	22			
OPTIONAL ASSESSMENTS (additional consent must be obtained)								

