9.2.2.1 SPEP, UPEP, SFLC, SIFE, and UIFE

Serum protein electrophoresis, UPEP, SIFE, UIFE, and SFLC will all be conducted at the local laboratory. Samples will be collected every 28 ± 7 days (starting from cycle 1 day 1) irrespective of cycle duration including dose delays and treatment discontinuation. Blood will be obtained for SFLC, SPEP, and SIFE. Twenty-four-hour urine samples will be obtained for UPEP and UIFE. Results for SPEP, UPEP, or SFLC must be available at screening and before enrollment. Serum protein electrophoresis, UPEP, and SFLC will be repeated on cycle 1 day 1 (unless screening values are within 14 days of cycle 1 day 1). Post cycle 1 day 1, UPEP and UIFE will be measured every disease assessment as well as SPEP and SIFE. Subjects with IgA, IgD, or IgE myeloma must have a quantitative IgA, IgD, or IgE (as appropriate) with each response assessment.

Subjects will be evaluated for disease response and progression according to the IMWG response criteria in Section 12.11 (Kumar et al, 2016). Disease status categories include sCR, CR, VGPR, PR, SD, and PD.

The following confirmation assessments are required for all response categories (sCR, CR, VGPR, PR, and progression*); refer to definitions in Section 12.11):

* Every effort should be made to obtain 2 consecutive samples at any time prior to initiation of any new therapy. If not possible to obtain the second consecutive assessment to confirm disease progression before initiation of any new therapy, this confirmatory sample for disease progression may be obtained after the new therapy is initiated.

- all response categories require 2 consecutive assessments made at any time before initiation of any new therapy
- all categories other than progression also require no known evidence of progression including new bone lesions if radiographic studies were performed
- confirmation of CR or better requires bone marrow assessment (aspirate or biopsy per IMWG-URC guidelines)

- extramedullary plasmacytoma evaluation (if present at screening)
- a second assessment is not required for radiographic and bone marrow assessments

Disease parameters needed to determine disease response, progression, and IRC adjudication will be collected via patient eCRFs and reviewed by the IRC.

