4.2 Subgroups

ORR and PFS will be examined for the below subgroup analysis. When there is not a sufficient number of subjects in the subgroup, i.e., less than 10% of the whole population, the subgroup analysis will not be conducted:

- prior carfilzomib exposure (yes, no)
- number of prior lines of therapy (1, 2)
- timing of lenalidomide refractoriness (during maintenance: yes, no)
- **Cytogenetic risk measured by FISH (high risk (t(4;14), t(14;16), deletion 17p), standard risk)**
- **R-ISS (stage I, stage II, stage III)**
- **Prior anti-CD38 exposure (yes, no)**
- **Refractory to prior anti-CD38 treatment (yes, no)**
- **Prior bortezomib exposure (yes, no)**
- **Refractory to prior bortezomib treatment (yes, no)**

5. Definitions

Baseline

The baseline value is defined as the last assessment prior to the first dose of **any study treatment**. Absolute change from baseline will be defined as (post baseline value - baseline value). Relative change from baseline will be defined as (post baseline value - baseline value)/baseline value * 100%.

Complete Response Rate (CRR)

CRR is defined as the proportion of subjects whose best overall response is sCR or CR.

Cytogenetic Risk group as determined by Fluorescent in Situ Hybridization (FISH)

The FISH data will be used to determine the cytogenetic risk group as following:

High risk group: Subjects who have the cytogenetic abnormalities t(4;14) or t(14;16), and/or deletion 17p.

Standard risk group: Subjects who do not have any of the cytogenetic abnormalities t(4;14), t(14;16) and deletion 17p.

Missing: Subjects who cannot be identified as high risk nor standard risk.

Duration of Response (DOR)

DOR is defined as the time from first evidence of PR or better per IMWG-URC to the earliest of disease progression or death due to any cause for subjects with a best response of PR or better. DOR will be censored as per the PFS endpoint. Please see [Table 5-1](#)

$$\text{DOR} = [(\text{PD or death date whichever occurs first}) \text{ or date of censoring if censored} - \text{response start date} + 1] / 30.4.$$

End of Study

The end of study date is defined as the date when the last subject across all sites is assessed or receives an intervention **for evaluation in the study (ie, last subject last visit), including any additional parts in the study (eg, long-term follow-up, additional antibody testing), as applicable.** The study will end 4 years after the last subjects is enrolled in the study.

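### As printed in Appendix 11, the sCR marrow rule fails lambda subjects whose kappa/lambda ratio is between 1:1 and just under 2:1, and the protocol names the specimen inconsistently; only the sCR/CR split can be affected

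*Protocol*

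**What the plan says.** The sCR row of Protocol Section 12.11 (Appendix 11) requires, among other items, "Absence of clonal cells in bone marrow biopsy by immunohistochemistry". It expresses this as a kappa/lambda ratio of at most 4:1 or at least "2:1 for kappa and lambda subjects respectively, after counting" at least 100 plasma cells. One ratio, kappa over lambda, therefore serves both limbs: an upper limit of 4:1 for kappa subjects and a lower limit of 2:1 for lambda subjects.

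Four places name the specimen:

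- The sCR row itself: biopsy, by immunohistochemistry.
- Table 2-1 (Schedule of Activities): "Bone marrow biopsy is required to confirm sCR".
- The footnote to Appendix 11: "For sCR: presence/absence of clonal cells is based upon the kappa/lambda" ratio, and the sentence goes on to place that ratio in aspirate.
- Section 9.2.2.1: "confirmation of CR or better requires bone marrow assessment (aspirate or biopsy per IMWG-URC guidelines".

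The sCR row also mentions aspirate, but for the separate requirement of fewer than 5% plasma cells, so that mention does not explain the footnote.

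The CR row has no marrow kappa/lambda test. Its only light-chain condition is "In subjects with baseline measurable disease only by SFLC, normal SFLC ratio". The SAP does not restate or amend the marrow rule.

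**The concern.** The test is meant to show that the subject's own clone is gone. For a lambda subject, residual clone pushes kappa/lambda down, so a lower limit is the right kind of limit. A lower limit of 2:1, however, requires kappa cells to outnumber lambda cells two to one. A lambda subject with an even mix, or with a clear kappa majority of 60 to 40, would be recorded as still having clonal lambda cells. The same 60/40 marrow passes in a kappa subject. The two limbs are not parallel: one tolerates a four-fold excess of the involved type, and the other demands a two-fold excess of the uninvolved type.

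This is operative text. Protocol Sections 5.1, 9.2.2 and 9.2.2.1 direct response assessment to Section 12.11, and sCR is one of the disease status categories listed in Section 9.2.2.1. If the printed bound is applied, sCR is under-recorded in one light-chain group for a reason unrelated to disease. If some assessors apply it and others apply the cited criteria, their sCR calls will disagree for the same reason. The specimen wording adds a second source of disagreement, because an assessor following the footnote could accept an aspirate ratio that Table 2-1 does not accept.

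**Working it through.** **Inputs from the documents.** At least 100 plasma cells counted (100 used here); kappa limb kappa/lambda ≤ 4; lambda limb kappa/lambda ≥ 2 (all from the sCR row).

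**Assumed input.** The true kappa share p of plasma cells in a marrow free of clone. The documents give no value, so a range is shown.

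**Step 1: cut-offs as cell counts.** Let K be the number of kappa cells among 100.

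- Lambda limb: K/(100 − K) ≥ 2 gives K ≥ 66.7, so K ≥ 67. Check: 67/33 = 2.03 passes; 66/34 = 1.94 fails.
- Kappa limb: K/(100 − K) ≤ 4 gives K ≤ 80. Check: 80/20 = 4.00 passes; 81/19 = 4.26 fails.

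| Kappa/lambda cells | Ratio | Lambda excess? | Lambda subject meets rule? | Kappa subject meets rule? |
|---|---|---|---|---|
| 50/50 | 1.00 | no | no | yes |
| 55/45 | 1.22 | no | no | yes |
| 60/40 | 1.50 | no | no | yes |
| 66/34 | 1.94 | no | no | yes |
| 67/33 | 2.03 | no | yes | yes |
| 80/20 | 4.00 | no | yes | yes |

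The wrongful failure covers ratios from 1:1 to just under 2:1 (K from 50 to 66). Lambda subjects at 2:1 or above pass.

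**Step 2: chance that a polyclonal marrow passes.** With K ~ Binomial(100, p), the lambda limb passes with probability P(K ≥ 67) and the kappa limb with P(K ≤ 80).

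| Assumed kappa share p | True ratio | Lambda limb passes | Kappa limb passes |
|---|---|---|---|
| 50% | 1.00 | 0.04% | > 99.9% |
| 60% | 1.50 | 9.1% | > 99.9% |
| 65% | 1.86 | 38.0% | > 99.9% |
| 66.7% | 2.00 | 51.9% | 99.9% |
| 70% | 2.33 | 77.9% | 99.1% |
| 75% | 3.00 | 97.2% | 90.0% |

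**Step 3: which outputs use the distinction.** A subject failing only this test still meets the CR row.

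- ORR counts PR, VGPR, CR and sCR together.
- CR-or-better pools the two: "CRR is defined as the proportion of subjects whose best overall response is sCR or CR" (SAP Section 5).
- MRD[-]CR counts sCR as CR (SAP Section 5).
- DOR and time to response start at PR or better; PFS and OS do not use sCR.
- Power does not depend on the split. As a side check, the Clopper-Pearson 90% lower-bound rule reproduces all eight powers in Protocol Table 10-1; for example, 52 subjects with at least 38 responders gives 91.8% at an ORR of 80%.

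What remains is the distribution of best overall response between sCR and CR. Under Protocol Section 10.4.2.1 and SAP Section 9.1, categorical variables are summarised by count and percentage in each category.

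**The case against.** The strongest reply is that nothing the trial sets out to estimate is touched. No objective, hypothesis or row of SAP Tables 9-1 and 9-2 isolates sCR. That is correct, and it limits the point to a descriptive split.

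Second, a reader might infer that lambda subjects have already been misclassified. The documents do not show this. Appendix 11 presents itself as a summary and lists its sources; the IRC works to the IMWG criteria under a charter that is not part of these documents; and ORCA's coding is not described. Misapplication is possible because Section 9.2.2.1 points to Section 12.11, but it is not demonstrated.

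Third, a reader might conclude that the bound is simply inverted and should read 1:2. That is a plausible guess, but the documents contain no other lambda cut-off and no normal marrow ratio, so they do not supply a replacement. It can also be said that 1:1 is not necessarily the right reference for an excess. That stands, but it does not rescue the printed bound: if the clone-free ratio were itself 2:1, sampling of 100 cells alone would fail 48% of lambda subjects (100 − 52), against 0.1% of kappa subjects.

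Fourth, the size depends on the assumed kappa share. At 75% the lambda limb passes 97% of the time, and the kappa limb falls to 90%. This is also correct, and is why the whole range is shown.

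On the specimen, Table 2-1 is explicit that sCR needs a biopsy, and Section 9 of the protocol makes adherence to the schedule a requirement. That lowers the practical risk but leaves the footnote in conflict with the row it annotates.

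**Conclusion.** The point holds in a narrow form. The printed lambda cut-off does not do what the test is for: a bound against lambda excess cannot require a kappa majority. It denies sCR to lambda subjects with ratios from 1:1 to just under 2:1, not to every lambda subject without lambda excess. The probability that a clone-free lambda marrow passes runs from 0.04% to 97% over assumed kappa shares of 50% to 75%, with binomial sampling of 100 cells. The documents do not say how many of the 52 treated subjects have lambda disease and meet every other sCR condition, so the number who could move between categories cannot be estimated.

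The specimen for the clonality test is inconsistent across the row, the footnote, Table 2-1 and Section 9.2.2.1, and no text reconciles them.

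It would go too far to say that the primary or key secondary result is biased, or that reclassification has occurred. The first is excluded by the pooling of sCR with CR, and the second is not shown. This is a cheap correction worth making before the sCR/CR breakdown is reported.

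**What to change.** 1. Check the lambda cut-off in the sCR row against the response criteria cited under Appendix 11, and correct it.
2. Make the sCR row, its footnote, Table 2-1 and Section 9.2.2.1 agree on the specimen for the clonality test, again from the cited criteria. Section 9.2.2.1 can keep its general statement for CR if it says separately what sCR needs.
3. Ask the IRC, the investigators and the owner of the ORCA algorithm which lambda cut-off and which specimen they used, and record the answer in the SAP or the study report.
4. Only if the printed cut-off was applied, re-derive sCR versus CR for lambda subjects from the marrow results already held.

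The cost is a few wording changes and one query to the assessors, plus a re-derivation in lambda subjects if step 4 applies. The cut-off correction needs no new samples. If step 3 finds subjects with an aspirate ratio but no biopsy, rewording cannot supply the missing specimen; their number should be reported with the sCR/CR split.
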